10.3 Data Derivations and Definitions

The following definitions and derivations will be used for this study:

Baseline for all assessments will be considered as the last non-missing assessment prior to the first administration of clinical trial material (CTM).

Change from baseline will be calculated as:

Change = observed value – baseline value.

Study days on or after the initial dose of CTM will be computed as:

Study Day = Date – Study Drug Start Date + 1.

For pre-dosing dates, Study Day = Date – Study Drug Start Date.

Age will be calculated from the date of birth to informed consent date.

Treatment-emergent events will be considered as any event occurring after the first dose of treatment drug and prior to a subject's termination, withdrawal or completion of the study.

Prior medications will be those ended before the first study treatment.

Concomitant medications are those used on or after the date of first study treatment.

11.0 STUDY POPULATION

Unless otherwise stated, all study population analyses will be performed on the Safety Population.

11.1 Subject Disposition

Subject disposition will be presented for all subjects. The composition of the analysis populations and those who enrolled, completed or discontinued from the study will be summarized by dose cohort and overall with descriptive statistics. Reasons for early discontinuation will be presented with frequencies and percentages for all categories.

11.2 Demographic and Baseline Characteristics

Demographics and baseline characteristics listing will include date of birth, age, gender, ethnicity, race, and height and weight and BMI at screening. Each of these variables except date of birth will also be summarized with descriptive statistics.

11.3 Prior Disease medications/therapy and Concomitant Medications

Concomitant medications will be coded with the World Health Organization (WHO) drug dictionary. Concomitant medications will be summarized with descriptive statistics by drug Anatomical Therapeutic Chemical (ATC) Classification System (level one), generic name, and cohort. A data listing will be included that shows all medications by generic name and verbatim name. Prior medications/therapy will be excluded from the summary but be included in the listing.

11.4 Concomitant procedures

Concomitant procedures will be summarized by indication type, treatment arm, and time point and also will be included in the listing.

11.5 Medical and Surgery History

Medical history will be summarized with descriptive statistics by medical history code and treatment group. A comprehensive data listing will also be included.

11.6 Inclusion/Exclusion Criteria

Inclusion and exclusion criteria failures will be included in a data listing.

11.7 Protocol Violations/Deviations

Protocol violations will be summarized with descriptive statistics by category. A listing of all events will also be included.

Major protocol deviations include, but are not limited to the following:

- Non-fulfillment of all inclusion criteria or fulfillment of at least one exclusion criteria;
- No consent form found;
- Other relevant deviations, to be judged on an individual basis.

Minor protocol deviations include, but are not limited to:

- Measurements obtained outside the visit window to a limited degree;
- Other deviations will be judged on an individual basis.

12.0 EFFICACY ANALYSIS

12.1 Tumor Assessment

Disease recurrence will be evaluated in this study using the Response Evaluation Criteria in Solid Tumors (RECIST) Version 1.1 (Eisenhauer, Therasse et al. 009). RECIST response will be summarized with descriptive statistics.

Local and central radiology tumor assessment will be performed in this study, summary of the tumor assessment will be presented.

12.1.1 Radiology Tumor Assessment

Radiology tumor assessment will be performed within 4 weeks of the registration.

If the study agent is completed or discontinued before disease recurrence the subject will be followed for recurrence on the following schedule. Radiological assessment of disease status until disease recurrence (i.e., chest X-ray, (chest CT or MRI is acceptable), pelvic/abdominal CT or MRI) performed quarterly (every 3 months ±7 days). The methods used for prestudy assessments (e.g., CT or MRI) should be used throughout the study and if possible, the same equipment should be used each time.

Radiology tumor assessment will be summarized with descriptive statistics in a summary table. A detailed listing will be provided.

13.0 SAFETY

The safety population will be used for all the analyses of safety data.

13.1 Exposure to Study Drug

Study treatment dosing compliance will be summarized with descriptive statistics by treatment group. All exposure and compliance data will be provided in data listings.

13.2 Adverse Events

All reported terms (investigator descriptions) for AEs will be coded using the most recent version of the Medical Dictionary for Regulatory Activities (MedDRA) and summarized with frequencies and percentages by treatment group, system organ classification, and preferred term.

A treatment-emergent adverse event (TEAE) is an event that emerges during treatment, having been absent pretreatment, or worsens relative to the pretreatment state.

The following summaries will be presented with frequencies and percentage by treatment group, system organ classification, and preferred term:

- All AEs
- All TEAEs
- TEAEs leading to discontinuation from the study
- TEAEs by relation to study treatment
- TEAEs by CTCAE severity
- All serious TEAEs
- Serious TEAEs by relation to study drug
- TEAEs with fatal outcome

For all AE summaries, events will be counted only once for a given subject by primary SOC and preferred term. When an adverse event occurs more than once for a subject, the maximum severity and causality will be used.

All AEs will be included in comprehensive data listings. A separate listing will be included for AEs leading to discontinuation from study and AEs with fatal outcome.

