Autologous Vigil will be supplied by Gradalis, Inc. Irinotecan will be supplied by Clinigen. Temozolomide will be ordered per standard institutional practice.

Group A

- (i) oral temozolomide 100 mg/m² daily (Days 1 5, total dose 500 mg/m²/cycle),
- (ii) oral irinotecan 50 mg/m² daily (Days 1 5, total dose 250mg/m²/cycle), and
- (iii) Vigil 1.0 x 10⁶ cells/injection or cells/injection, intradermally on Day 15.

or

Group B

- (i) oral temozolomide 100 mg/m² daily (Days 1 5, total dose 500 mg/m²/cycle), and
- (ii) oral irinotecan 50 mg/m² daily (Days 1 5, total dose 250mg/m²/cycle).

One cycle equals 21 days.

Duration:

Subjects may receive repeat cycles of treatment until disease progression, unacceptable toxicity, withdrawal of consent or other criterion is met for discontinuation from study. Subjects randomized to Group A, Vigil will receive up to 12 doses depending upon the quantity of Vigil manufactured from the surgical specimen. Within 6 weeks of second relapse or progression, subjects randomized to Group B, will be allowed to cross-over (see Section 10.0) to receive single agent Vigil every 21 days. Subjects who cross-over may receive up to 12 doses of Vigil depending upon the quantity of Vigil manufactured. Cross-over must occur within 2 years of End of Treatment assessments of Group B enrollment. For subjects crossing over, no alternative therapies will be given between End of Treatment and cross-over.

Efficacy Assessments:

- Progression Free Survival (PFS)
- Objective Response Rate (ORR) (RECIST 1.1)
- Overall survival (OS)

Safety Assessments:

- Laboratory assessments
- Physical examination, performance status, height, weight, temperature, blood pressure, and pulse
- Toxicity: CTCAE v 5.0

Exploratory Assessments:

Circulating EWS FLI1 DNA detection and intratumoral immune function analysis including, but not limited to IFNγ-ELISPOT analysis.

Evaluation of baseline tumor microenvironment including, but not limited to immunohistochemical evaluation of tumor PD-L1 expression and tumor infiltrating lymphocyte (TIL) populations.

Statistical Considerations:

The planned sample size of 114 randomized subjects is based on the following assumptions for the PFS endpoint:

- 1:1 randomization;
- Accrual period of 12 months;
- Follow-up period of 6 months;
- Assumed control group median PFS of 6 months from randomization;
- Two-sided test at the alpha=0.0476 level of significance;
- Power 90%;
- Assumed hazard ratio (HR) of 0.45

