7.0 WITHDRAWAL

7.1 Discontinuation from Study Treatment

Treatment will be continued until progressive disease by RECIST 1.1. However, insofar as some patients in our early vaccine trials had increased survival despite initial, short-term volume increase. There is accumulating evidence that some subjects treated with immune system stimulating agents may appear to demonstrate progression of disease by conventional response criteria before demonstrating clinical objective responses and/or stable disease and ultimately survival benefit. It may be that enhanced inflammation within tumors initially leads to an increase in tumor size or newly visible small lesions. Over time, both the malignant and inflammatory portions of the mass may then decrease leading to overt signs of clinical improvement.

Therefore, selected subjects may be allowed to continue study therapy after investigatorassessed RECIST 1.1 progression and with agreement by the Gradalis medical monitor if the subject is determined to be deriving clinical benefit, tolerating study drug and meeting the following criteria:

- 1. Absence of symptoms and signs indicating clinically significant PD indicating disease progression.
- 2. No decline in ECOG performance status.
- 3. Absence of rapid progression of disease or of progressive tumor at critical anatomical sites (e.g., cord compression) requiring urgent alternative medical intervention.

If subsequent imaging shows an objective response or stable disease relative to baseline, treatment with study agents will continue. If subsequent imaging again shows PD, patients will be discontinued from study therapy.

Subjects will discontinue **study treatment** if any of the following occur:

- 1. Disease progression by RECIST 1.1 criteria.
- 2. The patient experiences unacceptable (≥Grade 3) toxicity felt to be related to treatment with the Vigil immunotherapy that persists for >3 weeks. Subjects would be discontinued from both Vigil and chemotherapy.
- 3. The subject experiences unacceptable (≥Grade 3) toxicity felt to be related to treatment with irinotecan/temozolomide that persists for >3 weeks. Vigil therapy may be continued in monotherapy.
- 4. Persisting Grade 3 or 4 toxicity unrelated to treatment, defined as failing to normalize within 3 weeks.
- 5. Any Grade \geq 3 allergic reactions related to Vigil.
- 6. Grade 2 autoimmune reactions unless there is evidence of clinical benefit.

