16.0 STATISTICAL CONSIDERATIONS

16.1 Sample Size Justification

This is an open label randomized controlled Phase III clinical trial. Information concerning the predicted survival of the control group is limited, based on rarity of disease and few published reports. However expert advisors in the EWS field estimate a conservative one-year survival rate of 25% in the chemotherapy control group. The one-year survival rate of 60% in the Vigil treated group is estimated from EWS patients treated on the Vigil phase 1 protocol. These estimates correspond to a hazard ratio (HR) of 0.383 favoring Vigil over control.

Assuming 1:1 randomization and the use of a two-sided log rank test at the alpha=0.0476 level of significance, 67 events will provide 90% power to detect an PFS HR of 0.45. Assuming a Group B (control group) median PFS of 6 months, a one-year accrual period, and a six-month follow-up period after randomization of the last subject, it is estimated that the total sample size (number of subjects) required to achieve 67 events is 114 (57 patients in each arm).

An unblinded interim analysis will be conducted by an independent data monitoring committee (IDMC) when 40 PFS events have occurred. Based on the results of this interim analysis, the planned sample size may be increased to 120 events. If the sample size is increased to 120 events, then the study will have approximately 90% power to detect a true HR of 0.55. Note that if the sample size is increased to 120 events, then the accrual period will be extended to 24 months, with a 6-month follow-up period after randomization of the last patient. Under these assumptions, it is estimated that approximately 164 patients will need to be randomized in order to achieve 120 events. Section 16.6 provides further details.

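### Adverse events are compared only as once-per-subject percentages although observation time differs between arms, so equal monthly risks can show unequal percentages, in a direction the documents do not fix

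*SAP*

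**What the plan says.** SAP 13.2 has adverse events coded and "summarized with frequencies and percentages by treatment group". It lists eight adverse event summaries, introduced by "The following summaries will be presented with frequencies and percentage by treatment group". Within each, "events will be counted only once for a given subject by primary SOC and preferred term". Each figure is therefore the share of subjects with at least one event over whatever time they were observed.

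SAP 13.1 says "Study treatment dosing compliance will be summarized with descriptive statistics by treatment group" and "All exposure and compliance data will be provided in data listings". It plans no by-arm summary of treatment duration or adverse event observation time. Neither document plans a person-time rate, a time-to-first-event analysis or a comparison over a common period.

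On treatment length, Protocol 7.1 states "Treatment will be continued until progressive disease by RECIST 1.1", and the Synopsis (Duration) states "Subjects may receive repeat cycles of treatment until disease progression". Protocol 8.4.1 limits on-study chemotherapy to 12 cycles, and Vigil to 4 to 12 doses depending on how much was manufactured. Protocol 16.1 sizes the trial so that "67 events will provide 90% power to detect an PFS HR of 0.45", with a control median of 6 months.

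The adverse event window is described in several places:
- Protocol 14.4 ends recording 30 days after the last Vigil dose. It gives no separate end for Group B subjects who have not received Vigil.
- SAP 10.3 runs the treatment-emergent window from first dose until the subject terminates, withdraws from or completes the study. It is not cut at cross-over, which Protocol 10.0 allows for Group B after progression.
- Protocol 9.0 moves subjects to quarterly response follow-up when the study agent stops, one listed reason being that the vaccine supply is used up. The follow-up column of Appendix B has no toxicity entry.

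**The concern.** A once-per-subject percentage grows with the time a subject is watched. When treatment ends at progression and one arm is expected to progress later, the arms are watched for different lengths of time, and the safety tables partly reflect the efficacy result. Group A is the control regimen plus Vigil, so even background chemotherapy toxicity with the same monthly risk in both arms need not show the same percentage. With an open-label add-on, that comparison feeds directly into the benefit-risk judgement.

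**Working it through.** **1. The plan's own figures.** Inputs from Protocol 16.1 and SAP 7.0: HR 0.45, two-sided alpha 0.0476, power 90%, control median 6 months, 12 months' accrual, 6 months' further follow-up.

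Events (Schoenfeld) = 4(1.981 + 1.282)² / (ln 0.45)² = 66.8, so 67 as stated. With exponential PFS and uniform accrual, the event probabilities are 0.729 (B) and 0.455 (A), mean 0.592. Then 67 / 0.592 = 113.1 subjects, against 114 stated. The planning figures reproduce and can be used for time to progression.

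**2. Time on treatment, if it ends at progression or after 12 cycles.**
- Progression hazards: λ_B = ln 2 / 6 = 0.1155 per month; λ_A = 0.45 × 0.1155 = 0.0520 per month (median 6 / 0.45 = 13.3 months).
- Limit: T = 12 × 21 = 252 days = 8.28 months.
- Mean time = (1 − e^(−λT)) / λ: 5.33 months (B), 6.73 months (A), ratio 1.26.

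**3. Percentage with at least one event.** Neither document gives an adverse event rate, so I assume a constant monthly hazard h, equal in both arms:

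P = h / (h + λ) × (1 − e^(−(h + λ)T)).

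| h per month | Group B | Group A | Difference (unrounded inputs) |
|---|---|---|---|
| 0.01 | 5.1% | 6.5% | 1.3 points |
| 0.02 | 10.0% | 12.5% | 2.5 points |
| 0.05 | 22.5% | 28.0% | 5.4 points |
| 0.10 | 38.6% | 47.1% | 8.5 points |
| 0.20 | 58.7% | 69.5% | 10.8 points |

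At 0.05 per month this is about 16 against 13 of 57 subjects.

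**4. Dependence on the true effect** (h = 0.05, Group B 22.5%). Group A shows 26.8% at HR 0.55, 26.2% at HR 0.61, 24.3% at HR 0.80 and 22.5% at HR 1.

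**5. The Protocol 14.4 window read literally.** Group A is observed to the earlier of progression and the last Vigil dose, plus 30 days. With n doses given on Day 15 of successive cycles, the last falls 14 + 21(n − 1) days after the start. For Group B I assume observation to progression or 12 cycles, plus 30 days, because no end is stated. With C the last-dose time (A) or 8.28 months (B), and d = 30 days = 0.986 months:

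mean window = (1 − e^(−λC)) / λ + d

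P = 1 − e^(−hd) × [λ / (λ + h) × (1 − e^(−(λ+h)C)) + e^(−(λ+h)C)].

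| Doses in A | Mean window A | Mean window B | A at h = 0.10 | B at h = 0.10 |
|---|---|---|---|---|
| 4 | 3.4 months | 6.3 months | 28.4% | 44.4% |
| 8 | 5.6 | 6.3 | 42.3% | 44.4% |
| 10 | 6.6 | 6.3 | 47.4% | 44.4% |
| 12 | 7.6 | 6.3 | 51.5% | 44.4% |

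The sign changes between 8 and 10 doses. The distribution of doses is not given.

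**6. Cross-over time left in Group B.** Under the step 2 model, 1 − e^(−0.1155 × 8.28) = 61.6% of Group B progress within 12 cycles. If 75% of them cross over for 4 months (assumption), mean time in B is 5.33 + 0.75 × 4 × 0.616 = 7.18 months, longer than the 6.73 in A.

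**7. Effect of a rate.** Divide P by person-time to first event, (1 − e^(−(h+λ)T)) / (h + λ). At h = 0.05 that time is 4.51 months (B) and 5.59 months (A). The rates are 0.225 / 4.51 and 0.280 / 5.59, both 5.0 per 100 patient-months, so the ratio is 1.00; the crude ratio was 28.0 / 22.5 = 1.24.

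**8. A Cycles 1-4 percentage** (84 days = 2.76 months). By then 27% of B and 13% of A have progressed. The step 3 formula gives 11.1% against 12.0% (h = 0.05), 20.8% against 22.5% (0.10) and 36.9% against 39.8% (0.20), B first. A gap of 1 to 3 points remains.

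**The case against.** A reader might infer that the planned tables will make Vigil look more toxic than it is. The documents do not support that. It requires observation to follow treatment to progression, which is not what Protocol 14.4 or SAP 10.3 says, and steps 5 and 6 show the gap can shrink or reverse. It also requires Vigil to prolong PFS and the event risk to persist; events confined to early cycles would show less gap.

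It would also be too strong to call the percentages invalid. SAP 13.2 is descriptive and no between-arm adverse event test is planned, so no error rate is affected. The share of subjects with an event over the course they actually received is a legitimate quantity: longer treatment that brings more toxicity is a real consequence for the patient.

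The size is modest. The hazards are assumed, discontinuation for reasons other than progression is ignored, and with 57 per arm the gaps of 5.4, 8.5 and 10.8 points compare with standard errors of 8.1, 9.2 and 8.9 points. SAP 13.4 summarises laboratory results by arm and time point, which partly covers laboratory toxicity, and the listed exposure would allow rates to be computed later.

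All of this stands as a limit on the point, but none of it supplies a comparison that allows for unequal observation time. The uncertainty over the window is a further reason to define it and report it.

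**Conclusion.** The concern holds as a low-severity weakness in how safety is compared. Only once-per-subject percentages are planned, while observation time differs between arms and is neither aligned nor summarised. If observation follows treatment, the 12-cycle limit applies and HR 0.45 is true, Group A is treated about 26% longer and shows a 5 to 11 point excess for events with an equal constant hazard of 0.05 to 0.20 per month. The excess is 1 to 3 points for rarer events and none at HR 1. Under other readings of the documents' own windows the difference goes the other way, for example about 28% (A) against 44% (B) at 0.10 per month with four Vigil doses. The sign is therefore indeterminate, and no prediction that Vigil will look worse, or better, is justified. What is at stake is the reading of the safety tables.

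**What to change.** 1. Reconcile Protocol 14.4, SAP 10.3, the follow-up text of Protocol 9.0 and Appendix B, so that one adverse event observation window, with a stated end, applies to both arms. Report events in the cross-over period separately. This comes first, because a rate needs a defined denominator.
2. In SAP 13.1, summarise treatment duration and adverse event observation duration by arm.
3. In SAP 13.2, for treatment-emergent events overall, by CTCAE grade, serious and related, add beside each percentage the number of subjects with the event per 100 patient-months. Time at risk ends at the first event, the end of the aligned window or cross-over. Base between-arm safety statements on these rates and keep the percentages as description.
4. Optionally add the percentage within Cycles 1-4. It supplements the rates and cannot replace them, since a 1 to 3 point gap remains under the same assumptions.

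The cost is a clarification of the window and a few table columns. SAP 13.1 already provides for listing exposure data, and sample size and efficacy analyses do not change. The downside is that a person-time rate assumes a roughly constant hazard, so it describes events clustered in early cycles less well.

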- 8. Blood (PBMC) for immune function analysis (ELISPOT).
- 9. Plasma for immune function analysis (ctDNA).

Response Follow Up Assessments

If the study agent is discontinued (for reasons such as completion of all available doses of vaccine, intolerable toxicity, treatment interruption of more than 4 weeks, intercurrent illness, protocol deviation, at PI's discretion), the subject will be followed quarterly after the end of study visit until progression.

The following evaluations will be performed quarterly (every 3 months ±7 days) (unless otherwise specified):

- 1. A physical examination, including vital signs and body weight.
- 2. Assessment of concomitant medications taken.
- Radiological assessment of disease status with CT chest /abd/pelvis (MRI abd/pelvis may be substituted for CT abd/pelvis) must be collected. The methods used for prestudy assessments (e.g., CT or MRI) should be used throughout the study. If possible, the same equipment should be used each time.
- 4. A CBC with differential and platelet count.

- 5. Serum chemistries (creatinine, glucose, total protein, blood urea nitrogen (BUN), total carbon dioxide (CO2), albumin, total bilirubin, alkaline phosphatase, and aspartate transaminase (AST) and/or alanine transaminase (ALT)) and electrolytes (total calcium, chloride, potassium, sodium).
- 6. Blood collection for immune function analysis (ELISPOT) 3 months ±7 days from EOT and every 6 months ±7 days thereafter.
- 7. Assessment of Performance Status.

Long Term Follow Up

After progression, subjects and their physicians will be contacted quarterly for documentation of post study therapies and survival status.

As the intent-to-treat population includes all randomized patients, should a subject be randomized and choose to not receive any treatment on this study, the subject should be asked if he or she is willing to allow for survival follow up through phone call and/or physician contact quarterly. This follow up would include any anti-cancer therapies received and survival status information.

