14.4 Recording of an Adverse Event

Adverse events will be recorded for the duration of a subject's time on study: following procurement of the subject's tissue for tissue manufacture and for up to 30 days following the last administration of Vigil. All AEs, regardless of causal relationship are to be recorded in the eCRF and source documentation. Additional information about each event, such as treatment

required, eventual outcome, and whether or not therapy had to be interrupted or dosages reduced, will also be recorded on the eCRF.

Pre-existing conditions will be recorded at baseline on the Medical History Form. If a preexisting condition does not change, it does not have to be reported as an AE on subsequent cycles.

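### SAP 13.2 counts adverse events that lead to leaving the study, but the protocol's toxicity rules stop study treatment, so toxicity stops can go uncounted

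*SAP*

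**What the plan says.** SAP section 13.2 lists the planned adverse-event summaries. The one on discontinuation is "TEAEs leading to discontinuation from the study". The listing follows it: "A separate listing will be included for AEs leading to discontinuation from study and AEs with fatal outcome".

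Protocol section 7.1 concerns stopping study treatment. Its list opens "Subjects will discontinue study treatment if any of the following occur", and items 2 to 6 are toxicity criteria. Item 2 (persisting Vigil-related toxicity) ends everything: "Subjects would be discontinued from both Vigil and chemotherapy". Item 3 (persisting toxicity related to irinotecan/temozolomide) is different: "Vigil therapy may be continued in monotherapy".

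Protocol section 9.0 says what happens next. When the agent is stopped, with intolerable toxicity among the named reasons, "the subject will be followed quarterly after the end of study visit until progression". After progression, therapies and survival are documented quarterly.

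On data, section 7.1 requires the date of and reason for discontinuation on the eCRF. Section 14.4 collects, for each adverse event, its "eventual outcome, and whether or not therapy had to be interrupted or dosages reduced".

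Two other SAP outputs are relevant. Section 11.1 says that "those who enrolled, completed or discontinued from the study will be summarized by dose cohort and overall", and adds frequencies of reasons for early discontinuation. Section 13.1 summarises dosing compliance by treatment group and lists exposure data.

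**The concern.** Vigil is added to a two-drug chemotherapy backbone. A reader of the safety section will want to know whether adding it makes patients stop or cut any part of the regimen. The usual place to look is the table of adverse events leading to discontinuation. Here that table is keyed to leaving the study, whereas the protocol's toxicity rules act on treatment and keep the patient under observation.

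A low count could therefore be taken as good tolerability when it partly reflects good follow-up. Two programmers could also build different tables from the same SAP line. Interruptions and dose reductions matter for the same reason. Protocol section 7.2 ties chemotherapy delay to Vigil delay, and section 8.4.1 provides for Vigil dose reduction after toxicity, yet no planned adverse-event table would show either.

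**Working it through.** The plan states no figure to reproduce. The check sets the SAP's table definition against the protocol's rules.

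1. **What toxicity stops.** Protocol 7.1 items 2 to 6 stop study treatment. Item 3 can stop chemotherapy alone, and section 8.4.1 repeats that Vigil may go on after irinotecan and temozolomide end.

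2. **Where the patient goes.** Under protocol 9.0 the patient enters quarterly response follow-up, then survival follow-up. SAP 12.1.1 makes the same distinction: a patient whose study agent is completed or discontinued before recurrence is still followed for recurrence. SAP 4.1 and 7.1 use terminating the study as a reason for censoring PFS, so there it means leaving assessment.

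3. **What the SAP table counts.** There are two readings. The literal one counts events that lead to leaving the study. The loose one takes study to mean protocol treatment as a whole.

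| What the adverse event leads to | Literal reading | Loose reading |
|---|---|---|
| Leaving the study altogether | counted | counted |
| All study treatment stopped, follow-up continues | not counted | counted |
| Chemotherapy stopped, Vigil continues | not counted | not counted |
| Interruption or dose reduction only | not counted | not counted |

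The third row can arise only in Group A. A Group B patient who stops chemotherapy for toxicity has no Vigil to continue, and cross-over requires radiologic progression (protocol 10.1). On the loose reading, the same chemotherapy stop would count in Group B but not in Group A if Vigil went on.

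4. **Whether another output fills the gap.** SAP 13.1 gives compliance, with no link to adverse events. SAP 11.1 may give counts of stops by reason, but not by adverse-event term or by drug. Its breakdown is by dose cohort, although the trial has a single planned Vigil dose. The remaining 13.2 tables (relation, severity, serious, fatal) report the events without the treatment action.

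5. **How large the omission is.** Let r be the proportion of an arm stopping a study drug for toxicity, and f the fraction of those stops that the table captures. The number missed per arm is 57 × r × (1 − f), where 57 is the planned arm size. The documents give neither r nor f. For scale only, assume r is 5% to 15%: 57 × 0.05 = 2.85 and 57 × 0.15 = 8.55 stops per arm. With f anywhere from 0 to 1, the share missed runs from 100% to 0%, so the number missed runs from 0 to about 9 per arm.

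6. **Whether the data exist.** Reason for discontinuation, interruption and dose reduction are collected. Section 14.4 does not name permanent stop, or which drug was stopped, as a field recorded per event.

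**The case against.** The strongest reply is that the protocol itself uses study loosely, so the SAP line may simply mean stopping protocol treatment. There is good evidence for this:

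- The Synopsis (Duration) lists unacceptable toxicity and withdrawal of consent beside any other criterion for discontinuation from study, as limits on repeat cycles.
- Section 8.4.1 calls chemotherapy beyond 12 cycles off study.
- Section 9.0 places response follow-up after an end-of-study visit.
- Section 14.4 describes time on study for adverse-event recording as ending 30 days after the last Vigil dose.
- Section 15.1 speaks of discontinuing a patient on study for a serious or unexpected event.

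The eCRF wording that might settle the matter is not in the documents. It is also fair to say that the information is not lost. All adverse events are listed, the reason for stopping is recorded, and SAP 11.1 plans reasons for early discontinuation. The named safety endpoints (protocol 16.5, SAP 8.2) do not include treatment discontinuation.

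This stands as far as it goes. A reader might infer that the table would miss nearly every toxicity stop, show almost none in either arm whatever happened, or leave such patients out of every planned output. The documents do not support those readings: f is unknown, the term is ambiguous, and 11.1 may count stops by reason. Nor do they show that the data monitoring committee would see the same figures, since protocol 11.7 leaves its methods to a charter still to be developed.

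The reply does not remove the point. On the loose reading, a chemotherapy stop with Vigil continuing is still not a discontinuation from the study. The ambiguity is itself a reason to define the term.

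**Conclusion.** The mismatch is real and should be corrected. Read literally, the table and listing in SAP 13.2 omit toxicity stops in patients who remain in follow-up. On either reading they omit chemotherapy stops where Vigil continues, and no planned output links adverse events to treatment stops by drug.

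The size cannot be derived from the documents. The 0 to about 9 patients per arm shown above rests on an assumed 5% to 15% rate and an unknown capture fraction, and is not an estimate of what will be missed. A false tolerability conclusion is a risk of the wording, not a demonstrated outcome. The effect is confined to descriptive safety reporting. The PFS test, its alpha and patient management are untouched.

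**What to change.** - In SAP 13.2 and its listing, tabulate treatment-emergent events leading to discontinuation of study treatment by treatment group: any component, Vigil, and irinotecan/temozolomide. Keep events leading to discontinuation from the study as a separate line, and define both terms.
- Add tables of treatment-emergent events leading to interruption or dose reduction, from the fields collected under protocol 14.4.
- In SAP 11.1, report treatment discontinuation and study discontinuation separately, by randomised arm.
- Confirm that the eCRF records permanent stop by component, since 14.4 names only interruption and reduction.
- Align the protocol's use of study and study treatment in the Synopsis and in sections 8.4.1, 9.0, 14.4 and 15.1.

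The cost is SAP wording, a few extra descriptive tables and possibly one eCRF field check. No clinical stopping rule changes.
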